GCS Co., Ltd.	GANA V [®]	Final version 5.0	Confidential
	CIP #21E0787	Date: 27/06/2022	Page 1/6

OVERALL SYNOPSIS OF THE CLINICAL INVESTIGATION # 21E0787

ANSM registration #:	2021-A02451-40				
Clinical investigation plan #:	21E0787				
Title of the clinical investigation:	Clinical study for the safety and effectiveness of use of an injectable medical device GANA $V^{\mbox{\tiny B}}$ for facial aesthetic treatment				
Sponsor:	GCS Co., Ltd. [name]				
Development phase	Post market study Interventional Device used according to Instruction For Use (IFU)				
Objectives:	 The primary objective is to evaluate the effectiveness of Gana V[®] in comparison with Sculptra[®] in the correction of Nasolabial Folds (NLFs) 6 months after treatment initiation. The secondary objectives of the study are: To evaluate the effectiveness of Gana V[®] in comparison with Sculptra[®] in the correction of Nasolabial Folds (NLFs) 1^{1/2}, 3, 9, 12, 18 and 24 months after treatment initiation. To evaluate the effectiveness of Gana V[®] in comparison with Sculptra[®] on the global aesthetic improvement 1^{1/2}, 3, 6, 9, 12, 18 and 24 months after treatment initiation. To evaluate the effectiveness of Gana V[®] in comparison with Sculptra[®] on the global aesthetic improvement 1^{1/2}, 3, 6, 9, 12, 18 and 24 months after treatment initiation. To evaluate the effectiveness of Gana V[®] in comparison with Sculptra[®] in reducing NLFs depth and volume 1^{1/2}, 3, 6, 9, 12, 18 and 24 months after treatment initiation. To evaluate the subject satisfaction with Gana V[®] in comparison with Sculptra[®] 1^{1/2}, 3, 6, 9, 12, 18 and 24 months after treatment initiation. To evaluate the injector satisfaction with Gana V[®] in comparison with Sculptra[®] 1^{1/2}, 3, 6, 9, 12, 18 and 24 months after treatment initiation. To evaluate the injector satisfaction with Gana V[®] in comparison with Sculptra[®] after initial injection and touch-up injection if applicable. To evaluate the safety of Gana V[®] in comparison with Sculptra[®]. 				
Design:	 The study will be: double-blinded, randomized, within-subjects: each subject testing both devices, versus comparator, single centre. 				
Planned Sample Size:	55 subjects randomized.				
Number of investigational study sites:	1 site (France)				
Inclusion criteria:	 Healthy Subject Sex: male or female Age: between 30 and 70 years. Subject with moderate to severe nasolabial folds as determined by a Wrinkle Severity Rating Scale (WSRS) score of 3 or 4 on both folds at the pre-treatment evaluation. 				

GCS Co., Ltd.	GANA V [®] CIP #21E0787	Final version 5.0 Date: 27/06/2022	Confidential Page 2/6
	fillers, to peels, n period. 6. Subject, informati 7. Subject consent. 8. Subject v 9. Subject a 10. Female regimen	xin treatments, laser, micr on-invasive skin-tightening psychologically able to ur on and to give a written info having given freely and willing to have photographs affiliated to a health social s of childbearing potential s	expressly his/her informed of the face taken. ecurity system. should use a contraceptive ice at least 12 weeks before
Exclusion criteria:	 study. 2. Subject with face of the f	with a scar, moles, pigmen which might interfere with the who had been deprive rative or legal decision or w in a social or sanitary estable participation to another res an exclusion period of one having received 4500 tion in research involving months, including participal suspected to be non-co tor's judgment. suffering from a severe or p thology that may interfere sults.	ed of their freedom by ho is under guardianship. lishment earch on human beings or euros indemnities for human beings in the 12 tion in the present study. mpliant according to the progressive disease or any with the evaluation of the

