Study Procedures:	CIP #21E0787 "Imp acco - Meat 3, 6, fring - Prop mon - Injec and Secondary s Investigation Injection Site the study by their subject A screening On D0, base photographs receive a firs randomizatio satisfaction Adverse Ev immediately A month and scoring, fring before touch injector's tre touch-up inje subject opin before and a	Date: 27/06/2022 roved", "Much improved" or ording to GAIS. In change in NLF depth and 9, 12, 18 and 24 months at e projection system. Nortion of satisfied subjects ths after treatment initiation stor's satisfaction regarding touch-up injection using a q afety endpoints: al devices safety will be Reactions (ISRs) and Adve the investigator. Subjects diaries. visit will allow to inform and eline scoring (WSRS), fringe will be done before inje t injection of the investigation on list. Immediately after in will be collected. Investig rents (AEs) and Injection after injection. d a half after initial injection ge projection acquisitions ar -up (if applicable). Subject' atment satisfaction (if app ction will be made if necessa- ion. Investigator evaluator fter touch-up if applicable.	"Very much improved" score volume from baseline to 1 ^{1/2} , fter treatment initiation using 1 ^{1/2} , 3, 6, 9, 12, 18 and 24 using a questionnaire. injection quality after initial questionnaire. assessed by collection of erse Events (AEs) throughout will record ISRs and AEs in preselect the subjects. e projection acquisitions and ction. Eligible subjects will onal devices according to the njection, injector's treatment gator evaluator will collect on Site Reactions (ISRs) n (M1 ^{1/2}), WSRS and GAIS nd photographs will be done s treatment satisfaction and licable) will be collected. A ary, according to injector and will collect AEs and ISRs
	twenty-four((WSRS and photographs	M24) months after initial inju I GAIS scales), fringe p	(M12), eighteen (M18) and ection, effectiveness scoring projection acquisitions and eatment satisfaction will be ect AEs and ISRs
Otatiatia - Love the L		nary evaluation criterion:	
Statistical methods:	The parame level scores (statistics for deviation, firs	ter Wrinkle Severity Rating (at D0 before injection and N quantitative variable (N, st and third quartile, minimu	g Scale (WSRS) with the 5 /6) will be summarized using , mean, median, standard um and maximum value) for le from baseline (M6-D0bef)
	Inferential a	nalysis for the primary en	idpoint:

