	if the upper-		culptra [®] will be demonstrated CI of the (M6-D0bef) mean
	For the seco	ondary evaluation criteria:	.
	All the variab to their type For quantitat	oles will be described using (quantitative data or qualitat	adapted statistics according tive data). ired t test will be applied to

GCS Co., Ltd.	GANA V [®] CIP #21E0787		Final version 5.0 Date: 27/06/2022	Confidential Page 5/6
For qualitative data a McNemar's test will be applied t proportion of improvement or satisfaction between the The bilateral approach will be used with a significance				n between the products.
Foreseen study duration:		Clinical inves Clinical inves	tigation beginning: Q1 202 tigation end: Q2 2024 tigation global duration: 28 ubject: 24 months + screer	months

GCS Co I th	idential ge 6/6
-------------	--------------------

FLOW-CHART							1		
Procedure	Visit 1 Screenin g	Visit 2 Day 0	Visit 3 M1 ^{1/2}	Visit 4 M3	Visit 5 M6	Visit 6 M9	Visit 7 M12	Visit 8 M18	Visit 9 M24
Days	D-x	D0	D40 ±2	D90 ±2	D180 ±4	D270 ±4	D365 ±7	D540 ±14	D730 ±14
Informed consent form signature	•								
Medical examination	•								
Medical history and previous and concomitant treatments collection	•								
Checking of the inclusion and exclusion criteria	•								
Pregnancy test		●b							
Confirmation of eligibility		●b							
Randomization		•							
WSRS live assessment by a blinded evaluator	•	●b	●b	•	•	•	•	•	•
Macrophotographs		●b	●b	•	•	•	•	•	•
Fringe projection acquisitions (2 areas)		●b	●b	•	•	•	•	•	•
Injection + anaesthesia (if necessary)		•	Touch up						
GAIS live assessment by a blinded evaluator			●b	•	•	•	•	•	•
GAIS assessment by the subjects			●b	•	•	•	•	•	•
Subjective evaluation questionnaire for subjects			●b	•	•	•	•	•	•
ISR assessor		●a	●b+a	•	•	•	•	•	•
ISR subjects		completed each day during 4 weeks after injection and touch up if applicable at home by the subject							
Subjective evaluation questionnaire for injector		●a	●a						
AE and concomitant treatments and procedures collection	•	•	•	•	•	•	•	•	•
Study end									•

Keys:^b: Before injection; ^a: After injection

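### Does the secondary objective on injector satisfaction out to 24 months need changing, given that the injector questionnaire is filled in only at the two injection occasions?

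*Combined protocol and SAP*

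**What the plan says.** The document is a six-page synopsis with a flow chart. It deals with injector satisfaction in four places.

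- **Synopsis, Objectives.** There are two separate secondary objectives. One covers seven follow-up visits: "To evaluate the injector satisfaction with Gana V[®] in comparison with Sculptra[®] 1^{1/2}, 3, 6, 9, 12, 18 and 24 months after treatment initiation". The next covers the injections themselves: "To evaluate the injector satisfaction with Gana V[®] in comparison with Sculptra[®] after initial injection and touch-up injection if applicable".
- **Synopsis, Endpoints.** There is one injector endpoint. The text is broken across columns, but its fragments ("stor's satisfaction regarding touch-up injection using a q" and "injection quality after initial questionnaire") show a questionnaire on injection quality, completed after the first injection and after the touch-up. No later visit is named.
- **Synopsis, Study Procedures.** Injector satisfaction is collected straight after the D0 injection and, where applicable, at M1½.
- **Flow chart.** The row "Subjective evaluation questionnaire for injector" is marked at Visit 2 (D0) and Visit 3 (M1½) only, both with the key for after injection. Visits 4 to 9 are blank. The matching row for subjects is marked at every visit from M1½ to M24.

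**The concern.** An objective that names a between-product comparison at seven visits should have an endpoint and data behind it. This one seems to have neither at six of them. If the line is taken at face value, the sponsor would have to report the objective as not assessed, drop it once the data are known, or fill it from a source nobody planned. Each would leave a visible gap between plan and report.

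M1½ raises a second worry. The injector completes a form there only after a touch-up, and the touch-up is given when the injector and the subject think it necessary. Any M1½ comparison would then rest on a subset of the 55 subjects chosen after randomization, partly by the person whose satisfaction is being measured.

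**Working it through.** The plan gives no figure to reproduce, so the check sets the time points side by side.

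| Time point | Follow-up objective | Injector questionnaire in flow chart | Subject questionnaire in flow chart |
|---|---|---|---|
| D0 | no | yes, after injection | no |
| M1½ | yes | yes, after touch-up | yes |
| M3 | yes | no | yes |
| M6 | yes | no | yes |
| M9 | yes | no | yes |
| M12 | yes | no | yes |
| M18 | yes | no | yes |
| M24 | yes | no | yes |

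**Count.** The objective names 7 time points and the injector row has 2 marks. They overlap at 1 (M1½), so 7 − 1 = 6 time points have no scheduled injector form. The objective's seven visits are exactly the seven visits of the subject questionnaire.

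**What depends on the line.** The only injector endpoint concerns injection quality at the two injections. That matches the second injector objective and the flow chart in full. The Statistical methods section plans paired t tests for quantitative secondary data and McNemar's test for proportions improved or satisfied. These apply to collected variables, and no injector variable is listed for M3 to M24. Without the follow-up bullet, the endpoints, planned tests, visits and forms all stay as they are.

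**Whether the line is reliable.** Three features of the text argue for caution:

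- The same list of objectives prints the global aesthetic improvement line twice, word for word.
- The bullet in question has the time points of the subject-satisfaction objective before it and the opening of the injector objective after it.
- The text as read contains evident garbled repetition elsewhere, in the exclusion criterion on filling products.

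A copy-and-paste carry-over by the sponsor or a fault in reading the PDF would each produce this pattern. The available text cannot tell the two apart.

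**M1½.** The objective tied to the injections already limits the second rating to cases where a touch-up is given. Injection quality cannot be rated where nothing was injected. Both planned tests are paired, so they use only subjects with a rating for each product. A separate restriction to subjects touched up on both folds would therefore add nothing.

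**The case for a change.** The strongest case for acting is that the two injector objectives stand as separate bullets, so the second cannot be read as clarifying the first. The flow-chart row is intact, and its blanks at M3 to M24 are not a reading fault. This is a final version 5.0, and deleting one line costs almost nothing and would bring objectives, endpoint and schedule into agreement.

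Most of this stands as description: the mismatch is in the text as read, and the count of six is right. One link is weaker. The procedure text for the later visits is broken ("eatment satisfaction will be ect AEs and ISRs"), so it does not show by itself whose satisfaction is collected; the flow chart has to settle that.

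What does not stand is the consequence. No pre-specified analysis fails, because none was attached to the line. The argument for deletion also assumes that the long-term assessment was never wanted, which the documents suggest but do not prove.

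The point about a selected subset at M1½ is fair as a caution in reading the touch-up rating: it describes touched-up subjects and nobody else. The plan already says as much through its own condition. Relabelling that comparison as descriptive would be a preference set against the paired tests the plan specifies.

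**Conclusion.** This is a clerical inconsistency with nothing to gain from a change. One bullet names seven time points, and six have no scheduled injector data. No endpoint, planned test, visit or form depends on it. The primary analysis (WSRS change at 6 months), the sample size of 55 and the safety assessment are unaffected.

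An analyst would follow the endpoint and the flow chart: compare injector ratings after the first injection, compare them after the touch-up among those who had one on both sides, and state that no injector assessment was scheduled from M3 onward. A reader of the report would lose nothing the trial was set up to measure. Anyone holding the sponsor's own page can check whether the bullet is there and tidy it at a routine revision, but no result waits on that.

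The conclusion rests on two assumptions: that the flow chart reflects what is actually collected, and that no fuller plan outside this synopsis defines an injector endpoint at M3 to M24. If a fuller plan did define one, the flow chart would have to be reconciled with it.

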Comparator: Name / code Classification Composition Galenic form Administration route	Mannitol. Sterile freeze		,
Endpoints:	Mean chang treatment ini	tiation, as assessed by a	baseline to 6 months after in independent blinded live inkles Severity Rating Scale
	- Mean 24 m live in - WSF after inder with WSF - Glob 1 ^{1/2} ,	onths after treatment initiation ndependent evaluator. RS responder rates 1 ^{1/2} , 3, treatment initiation as a bendent evaluator. A respo at least 1-point improver RS. al Aesthetic Improvement S 3, 6, 9, 12, 18 and 24 mor	eline to 1 ^{1/2} , 3, 9, 12, 18 and ion as assessed by a blinded 6, 9, 12, 18 and 24 months ssessed by a blinded live nder is defined as a subject nent from baseline on the Scale (GAIS) responder rates of the after treatment initiation a blinded live independent

GCS Co., Ltd.	GANA V [®] CIP #21E0787	Final version 5.0 Date: 27/06/2022	Confidential Page 4/6
Study Procedures:	CIP #21E0787 "Imp acco - Meat 3, 6, fring - Prop mon - Injec and Secondary s Investigation Injection Site the study by their subject A screening On D0, base photographs receive a firs randomizatio satisfaction Adverse Ev immediately A month and scoring, fring before touch injector's tre touch-up inje subject opin before and a	Date: 27/06/2022 roved", "Much improved" or ording to GAIS. In change in NLF depth and 9, 12, 18 and 24 months at e projection system. Nortion of satisfied subjects ths after treatment initiation stor's satisfaction regarding touch-up injection using a q afety endpoints: al devices safety will be Reactions (ISRs) and Adve the investigator. Subjects diaries. visit will allow to inform and eline scoring (WSRS), fringe will be done before inje t injection of the investigation on list. Immediately after in will be collected. Investig rents (AEs) and Injection after injection. d a half after initial injection ge projection acquisitions ar -up (if applicable). Subject' atment satisfaction (if app ction will be made if necessa- ion. Investigator evaluator fter touch-up if applicable.	"Very much improved" score volume from baseline to 1 ^{1/2} , fter treatment initiation using 1 ^{1/2} , 3, 6, 9, 12, 18 and 24 using a questionnaire. injection quality after initial questionnaire. assessed by collection of erse Events (AEs) throughout will record ISRs and AEs in preselect the subjects. e projection acquisitions and ction. Eligible subjects will onal devices according to the njection, injector's treatment gator evaluator will collect on Site Reactions (ISRs) n (M1 ^{1/2}), WSRS and GAIS nd photographs will be done s treatment satisfaction and licable) will be collected. A ary, according to injector and will collect AEs and ISRs
	twenty-four((WSRS and photographs	M24) months after initial inju I GAIS scales), fringe p	(M12), eighteen (M18) and ection, effectiveness scoring projection acquisitions and eatment satisfaction will be ect AEs and ISRs
Otatiatia - Love the L		nary evaluation criterion:	
Statistical methods:	The parame level scores (statistics for deviation, firs	ter Wrinkle Severity Rating (at D0 before injection and N quantitative variable (N, st and third quartile, minimu	g Scale (WSRS) with the 5 /6) will be summarized using , mean, median, standard um and maximum value) for le from baseline (M6-D0bef)
	Inferential a	nalysis for the primary en	idpoint:
	if the upper-		culptra [®] will be demonstrated CI of the (M6-D0bef) mean
	For the seco	ondary evaluation criteria:	.
	All the variab to their type For quantitat	oles will be described using (quantitative data or qualitat	adapted statistics according tive data). ired t test will be applied to

GCS Co., Ltd.	GANA V [®] CIP #21E0787		Final version 5.0 Date: 27/06/2022	Confidential Page 5/6
For qualitative data a McNemar's test will be applied t proportion of improvement or satisfaction between the The bilateral approach will be used with a significance				n between the products.
Foreseen study duration:		Clinical inves Clinical inves	tigation beginning: Q1 202 tigation end: Q2 2024 tigation global duration: 28 ubject: 24 months + screer	months

GCS Co I th	idential ge 6/6
-------------	--------------------

FLOW-CHART							1		
Procedure	Visit 1 Screenin g	Visit 2 Day 0	Visit 3 M1 ^{1/2}	Visit 4 M3	Visit 5 M6	Visit 6 M9	Visit 7 M12	Visit 8 M18	Visit 9 M24
Days	D-x	D0	D40 ±2	D90 ±2	D180 ±4	D270 ±4	D365 ±7	D540 ±14	D730 ±14
Informed consent form signature	•								
Medical examination	•								
Medical history and previous and concomitant treatments collection	•								
Checking of the inclusion and exclusion criteria	•								
Pregnancy test		●b							
Confirmation of eligibility		●b							
Randomization		•							
WSRS live assessment by a blinded evaluator	•	●b	●b	•	•	•	•	•	•
Macrophotographs		●b	●b	•	•	•	•	•	•
Fringe projection acquisitions (2 areas)		●b	●b	•	•	•	•	•	•
Injection + anaesthesia (if necessary)		•	Touch up						
GAIS live assessment by a blinded evaluator			●b	•	•	•	•	•	•
GAIS assessment by the subjects			●b	•	•	•	•	•	•
Subjective evaluation questionnaire for subjects			●b	•	•	•	•	•	•
ISR assessor		●a	●b+a	•	•	•	•	•	•
ISR subjects		completed each day during 4 weeks after injection and touch up if applicable at home by the subject							
Subjective evaluation questionnaire for injector		●a	●a						
AE and concomitant treatments and procedures collection	•	•	•	•	•	•	•	•	•
Study end									•

Keys:^b: Before injection; ^a: After injection

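### Does an optional touch-up at M1½, before the M6 primary WSRS, call for a planned comparison of touch-up use between Gana V and Sculptra?

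*Combined protocol and SAP*

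**What the plan says.** The Study Procedures row describes the M1½ visit in text whose columns were split on extraction: "ction will be made if necessa- ion. Investigator evaluator fter touch-up if applicable", with the companion fragment "ary, according to injector and will collect AEs and ISRs". Read together, they say that a touch-up is given when necessary, on the opinion of injector and subject. The Flow-chart puts it at Visit 3 (D40 ±2). It also shows it to be optional, since the subject's reaction diary is "completed each day during 4 weeks after injection and touch up if applicable at home by the subject". The primary WSRS is read at Visit 5 (D180 ±4).

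The Objectives list is legible throughout. Touch-up appears there once, as injector satisfaction "after initial injection and touch-up injection if applicable". In the Statistical methods row the primary inference rests on an upper limit of the "CI of the (M6-D0bef) mean" change; the margin and confidence level cannot be read. McNemar's test is assigned to the "proportion of improvement or satisfaction between the" products, and a paired t test to quantitative outcomes.

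Two further entries bear on interpretation. The Development phase row states "Device used according to Instruction For Use (IFU"), and the objectives time every assessment from the start of treatment. The Flow-chart marks the M1½ WSRS, both GAIS ratings, the fringe projection and the subject questionnaire as taken before injection.

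**The concern.** Each subject receives both products, one per fold, and nothing legible requires the two folds to be touched up alike. If the decision is made fold by fold and follows visible response, the fold with the weaker first result tends to receive more product between D40 and D180. The M6 difference then moves toward zero, which helps a claim decided by an upper confidence limit. Blinding does not remove this, because the trigger is the response itself.

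At stake is what a positive result means. Readers may take it that Gana V performs as well as Sculptra for the same amount of treatment, when it may do so only with more re-treatment. No legible table or test would tell them which.

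**Working it through.** **Stated figure.** The only design figure is "55 subjects randomized". Its inputs (SD of the paired difference, margin, power, dropout) are not legible, so it can be neither reproduced nor refuted. The concern does not dispute it.

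**Effect of unequal touch-up.** Let D be the Gana V deficit in WSRS points without touch-up, x the excess share of Gana V folds touched up, g the gain per touch-up still present at M6, m the margin and SD the standard deviation of the paired difference. Only n = 55 comes from the synopsis; everything else is assumed, including a two-sided 95% interval.

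- True M6 difference: δ = D − g·x
- Chance of passing: Φ[(m − δ)·√55/SD − 1.96]

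Take the least favourable case, D = m. The formula becomes Φ[g·x·√55/SD − 1.96], and the margin drops out. For g = 1.0, x = 0.20, SD = 0.75: 0.20 × 7.416/0.75 = 1.978; 1.978 − 1.96 = 0.018; Φ = 0.51.

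| g·x | SD 0.5 | SD 0.75 | SD 1.0 |
|---|---|---|---|
| 0 (equal use, equal gain) | 2.5% | 2.5% | 2.5% |
| 0.10 (g = 0.5, x = 0.20) | 32% | 17% | 11% |
| 0.20 (g = 1.0, x = 0.20) | 84% | 51% | 32% |

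**What those percentages mean.** With m = D = 0.3 and g·x = 0.20, the true M6 difference is 0.3 − 0.20 = 0.10, which is inside the margin. A pass is then the correct answer for the treatment as delivered. For a false positive rate, set the true M6 difference equal to the margin, δ = m. The chance of passing is Φ(−1.96) = 2.5%, whatever x is. The excess over 2.5% is an error only for a different question: the effect had no touch-up been given. No objective asks that. The mechanism also runs both ways. If Sculptra folds needed more touch-up, x would be negative and the shift would count against Gana V.

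**What is already planned.** WSRS, GAIS, fringe projection and subject satisfaction at M1½ are between-product secondary outcomes, all taken before any touch-up and covered by the paired t test or McNemar's test. They show early response without re-treatment, though not how much re-treatment each product then received.

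**What a formal touch-up test would add.** Take exact McNemar on 55 pairs, with b and c the discordant counts and 95% half-width 1.96·√[(b + c) − (b − c)²/55]/55.

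| b : c | Difference | Half-width | p |
|---|---|---|---|
| 10 : 2 | 14.5 points | 11.7 | 0.039 |
| 12 : 4 | 14.5 points | 13.7 | 0.077 |
| 15 : 5 | 18.2 points | 15.2 | 0.041 |

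The same 14.5-point difference falls on either side of 0.05 according to the number of discordant pairs. The test would discriminate poorly, and it would be empty if both folds are always touched up together.

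**Timing.** The synopsis is version 5.0, dated 27/06/2022. A planned end in Q2 2024 with 24 months per subject puts the last D0 at about the end of June 2022. Adding 40 to 42 days puts the last touch-up near 11 August 2022, about 45 days after that date. On the planned schedule, a new per-fold case report form field could miss many of the M1½ visits.

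**The case for a change.** The best case for a change is that the Objectives list is complete, so the lack of a touch-up comparison is not merely an effect of damaged text. A regimen result is also easier to interpret when the amount of treatment on each side is shown, and early response at D40 is no substitute for that. Stating whether touch-up is decided per fold, and adding a table, would cost little.

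Part of this stands. The order of events is as described, and if folds are touched up separately, readers will want the counts by product. But exposure need not be an objective to be tabulated, and its absence from an objectives list in a six-page synopsis does not show that it will go unreported. The fold-by-fold premise appears nowhere in the documents. The trial is described as double-blinded; so far as that covers those who decide on touch-up, an imbalance would reflect response rather than knowledge of the product. No stated objective is left unanswered, and the primary analysis followed as written gives a valid result for the regimen.

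**Conclusion.** No change is needed. This is missing detail that analysts would normally supply: touch-up by product belongs in the exposure tables, by fold where recorded, and the M6 conclusion is naturally read as applying to initial injection plus touch-up as needed. The 11% to 84% range shows how far unequal re-treatment could move the M6 result on assumed gains and SDs. It does not measure error in the planned test, whose false positive rate under the stated assumptions stays at 2.5% for the regimen compared.

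This rests on two points: that the intended question is use under the device instructions, timed from the start of treatment, and that touch-up is recorded. Some record is implied by the injector questionnaire and reaction assessments tied to touch-up, although a per-fold record is not legible. The conclusion would differ if a pass were presented as equal effect for an equal amount of product, a claim the objectives do not make.

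### As far as the text is legible, the primary WSRS comparison uses the raw M6-minus-D0 change with no adjustment for the pre-treatment fold difference, so avoidable baseline reading error stays in the deciding confidence interval

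*Combined protocol and SAP*

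**What the plan says.** The Design row of the synopsis describes a randomized within-subject comparison, "each subject testing both devices", and the sample-size row plans "55 subjects randomized".

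The flow-chart row "WSRS live assessment by a blinded evaluator" is marked at Visit 1 (screening) and again at Visit 2 (D0), where the key letter b stands for "Before injection". The Inclusion criteria row asks for a WSRS "score of 3 or 4 on both folds at the pre-treatment evaluation", so both folds are scored before any product is given. It does not say whether that evaluation is the screening visit, D0 or both.

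The Statistical methods row summarises the five-level WSRS at D0 before injection and at M6, and defines change as M6 minus D0. The decision sentence is broken, but it refers to an upper limit and to the "CI of the (M6-D0bef) mean" change. For secondary quantitative endpoints the legible text gives a paired t test. No legible text uses the screening score in the primary analysis or adjusts for baseline.

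**The concern.** Each subject contributes one number: the change on one product's fold minus the change on the other's. Using raw change subtracts the full D0 fold difference, as if every observed grade of pre-treatment difference would persist to M6.

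That is unlikely here. The scale has whole grades and entry limits both folds to 3 or 4, so where that rule holds at D0 the fold difference can only be -1, 0 or +1. Part of any observed one-grade difference is rounding or reading error, which will not reappear at M6. Subtracting all of it adds noise.

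The conclusion turns on one confidence limit, so extra width costs power. Because sides are allocated at random, pre-treatment scores can be used as a covariate without favouring either product.

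**Working it through.** **Inputs.** From the documents: two blinded pre-treatment readings of both folds, five grades, entry at 3 or 4, 55 subjects, change defined as M6 minus D0. Not given or not legible: WSRS SD, reliability, margin, power, dropout, primary confidence level. The figure of 55 therefore cannot be reproduced. With n = (SD x (z0.975 + z_power) / margin)^2, assumed SDs of 0.5-0.9 and margins of 0.2-0.5 give anything from 8 to 159 subjects at 80% power and 11 to 213 at 90%.

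**Formulas.** Per subject, product A minus product B, let x be the D0 fold difference and y the M6 fold difference. Let T be the variance of the true pre-treatment fold difference, E the error variance of a fold difference at one visit, and F the variance of the fold-specific difference in effect. With independent errors:

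- raw change, y - x: F + 2E
- change from the mean of screening and D0: F + 1.5E
- y regressed on x: F + E + TE/(T+E)
- y regressed on the mean of the two pre-treatment differences: F + E + T(E/2)/(T+E/2)

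Raw change exceeds regression on D0 by E - TE/(T+E) = E^2/(T+E), which is never negative. Regression on D0 alone is at least as good as averaging whenever T is no larger than E.

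**One case by hand (all assumed).** True fold SD 0.25, so T = 2 x 0.0625 = 0.125. Effect SD 0.4, so F = 2 x 0.16 = 0.32. Reading-error SD 0.3 plus rounding variance 1/12, so E = 2 x (0.09 + 0.0833) = 0.3467.

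- raw change: 0.32 + 0.6933 = 1.0133, SD 1.007
- averaging: 0.32 + 0.52 = 0.84, SD 0.917 (9% smaller)
- regression on D0: 0.6667 + 0.0919 = 0.7586, SD 0.871 (about 13.5% smaller)
- regression on the two-reading mean: 0.6667 + 0.0726 = 0.7393, SD 0.860 (about 14.6% smaller)

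**Simulation.** The same model on a rounded five-grade scale with the entry rule applied gives these SDs of the paired difference:

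| Error SD | Error correlation, screening-D0 | Entry rule also at D0 | Raw change | Averaging | Regression on D0 | Regression on mean |
|---|---|---|---|---|---|---|
| 0.2 | 0 | no | 0.893 | 0.825 | 0.800 | 0.791 |
| 0.2 | 0.5 | yes | 0.877 | 0.842 | 0.803 | 0.797 |
| 0.3 | 0 | no | 1.002 | 0.902 | 0.863 | 0.856 |
| 0.3 | 0.5 | yes | 0.966 | 0.919 | 0.865 | 0.861 |
| 0.6 | 0 | no | 1.418 | 1.210 | 1.112 | 1.109 |
| 0.6 | 0.5 | yes | 1.270 | 1.202 | 1.117 | 1.115 |

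Regression on D0 narrows the interval by 10, 8, 14, 10, 22 and 12% in the six rows. Averaging narrows it by 8, 4, 10, 5, 15 and 5%. Adding the screening reading to the regression gives a further 0-1%.

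**Shared errors.** Two further sets of assumed scenarios let errors be shared between folds as well as between visits. In one (54 scenarios, correlations up to 0.8), regression on D0 gave 4-17%, averaging 3-10%, and regression was better in 48. In the other (48 scenarios, entry at 3 or 4 at both readings), regression gave 6-20%, averaging 4-10%, and regression did at least as well in all. After regression, the screening reading added 0-4.5% and 0-3% respectively.

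**At 55 subjects.** The 95% half-width is 1.96 x SD / sqrt(55). For the third row it is 0.265 grade with raw change, 0.238 with averaging and 0.228 with regression on D0. Estimating the slope multiplies the variance by about 1 + 1/(55 - 3) = 1.019, so the width grows by about 1% and 0.228 becomes about 0.230.

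**The case against.** D0 before injection is the customary baseline. Photographs and fringe projection also start there, so all effectiveness measures share it, and a paired change is easy to report. This stands: the plan's choice is valid, and nothing in it is biased or contradictory.

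The size of the gain rests wholly on assumptions. One evaluator scoring both folds of one face may make the same error on each, and shared error largely cancels in the paired difference. If the two folds score alike at D0 in every subject, nothing is lost. This also stands, and is why the range is wide.

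The decision sentence is incomplete, so an adjustment in the missing words cannot be excluded.

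A reader might infer that the unused screening score is the main cause, that baseline should be the mean of the two readings, and that this is worth some 10-29% more subjects. The documents do not support that:

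- The percentage comes from assumed, mostly independent errors.
- Most of the recoverable loss comes from the unadjusted change score; regression on D0 alone usually recovers more than averaging.
- The flow-chart gives the screening day only as D-x, and no legible text says the same evaluator scores both visits. Screening is where eligibility is checked, so scores there may be drawn towards the entry grades.
- A half-point baseline does not fit the 1-point responder rule in the Endpoints row: from 3.5, a score of 3 is an improvement of 0.5 and a score of 2 is 1.5.

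**Conclusion.** The point holds as a minor, optional gain in precision. As far as it can be read, the plan leaves removable baseline reading error in the interval that decides the trial. Adjustment would narrow that interval by about 4-20% for assumed error SDs up to about 0.5 grade (22% in the one more extreme case, at 0.6). The screening reading accounts for about 0-4% of this. In small samples, about 1% is given back for estimating the slope.

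These figures assume that reading error is not zero and is not fully shared between folds or across visits. The direction is firmer than the size: raw change is the regression with its slope fixed at 1, so apart from the cost of estimating the slope, adjustment cannot do worse.

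It would be wrong to infer that the trial is underpowered or that D0 biases the comparison. With no legible margin or SD, nobody can show that the narrower interval would change the decision. If the missing words already contain an adjustment, what remains is the small screening-reading gain.

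**What to change.** Before unblinding, prespecify the following.

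- For M6, regress each subject's between-product difference in WSRS score on that subject's pre-treatment fold difference, both taken as product A minus product B. Use as covariate either the D0 difference or the mean of the screening and D0 differences (D0 alone where screening is missing), and fix the choice in advance.
- Leave the covariate uncentred. The intercept and its confidence interval are then the primary estimate. With the D0 covariate, the intercept and interval are the same whether the outcome is the M6 score or the M6-D0 change, so the endpoint is unchanged. With the two-reading mean, use the M6 score as the outcome.
- If no subject has a D0 fold difference and D0 is the covariate, revert to the unadjusted paired interval.
- Use the same model for mean WSRS change at the other visits.
- Report the unadjusted M6-D0 paired interval as a sensitivity analysis.
- Keep D0 as the baseline for the responder definition.

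The cost is a few lines of text and an analysis slightly less simple than the raw paired change. It needs no new visit, reading or staff. If the full decision sentence already states an adjustment, the only question left is whether to add the screening reading to the covariate.
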